5.2. ATP cohort for analysis of immunogenicity

The ATP cohort for immunogenicity will include all subjects in the TVC:

- Who met all eligibility criteria.
- For whom the administration route and site of the vaccines was according to protocol.
- Who complied with the vaccination schedule.
- Who received the study vaccines according to protocol procedures.
- Who did not receive a concomitant medication/ product leading to elimination from the ATP analysis for immunogenicity up to the 1 month post-Dose 2 visit (Day 90).

Statistical Analysis Plan

Study alias & e-track number(s): NTHi-004 (200157)

- Who did not present with an intercurrent medical condition leading to elimination from the ATP analysis for immunogenicity up to the 1 month post-Dose 2 visit (Day 90).
- Who complied with the blood sample timings, at the 1 month post-Dose 2 visit (Day 90).
- For whom post-vaccination immunogenicity results are available for at least 1 assay.

5.3. ATP cohort for analysis of persistence of immunogenicity

The ATP cohort for persistence of immunogenicity (starting at Day 180) will include all evaluable subjects, *i.e.*, those who were included in the ATP cohort for immunogenicity, or were excluded from this cohort solely because they had no blood samples taken or because of incompliance with blood sample timings up to the 1 month post-Dose 2 visit, and:

- Who did not receive a concomitant medication/ product leading to elimination from the ATP analysis for immunogenicity.
- Who did not present with an intercurrent medical condition leading to elimination from the ATP analysis for immunogenicity.
- Who complied with the blood sample timings after the 1 month post-last vaccination visit.
- For whom persistence immunogenicity results are available for at least 1 assay.

5.4. ATP cohort for analysis of efficacy

The ATP cohort for analysis of efficacy will include all subjects in the TVC:

- Who met all eligibility criteria.
- For whom the administration route and site of the vaccines was according to protocol.
- Who complied with the vaccination schedule
- Who received the study vaccine according to protocol procedures.
- Not having received a medication/ product/ vaccine that may lead to elimination from the ATP analysis for efficacy.

The list of applicable elimination codes for each cohort can be found in the study specific form FORM-BIO-CLIN-9004-05 Criteria for eliminating subjects from the analyses.

Cohort	Elimination codes	Eli Type
ATP cohort for analysis of immunogenicity	1010-2500	MA

Statistical Analysis Plan

Study alias & e-track number(s): NTHi-004 (200157)

ATP cohort for analysis of efficacy	1010-2500	EF
ATP cohort for analysis of persistence of immunogenicity	1010-2500	FU

6. STATISTICAL METHODS

6.1. Analysis of demographics

Demographic characteristics (age at the first dose in years, gender and geographical ancestry), cohort description and other characteristics such as smoking/exposure history status, pulmonary function test baseline results and COPD history, history of exacerbation present/past medical history/intercurrent morbidity, and previous vaccination with a pneumococcal vaccine or an influenza vaccine will be summarized by group using descriptive statistics:

- Frequency tables will be generated for categorical variable such as geographical ancestry;
- Mean, median and standard error will be provided for continuous data such as age.

Other characteristics such as height, weight, BMI selected results and several risk factors from the six-minutes-walk test, and distribution of several severity stages using CAT or mMRC or SGRQ-C at enrolment visit will also be summarized.

The number of subjects enrolled into the study as well as the number of subjects excluded from ATP analyses will be tabulated.

The distribution of subjects enrolled among the study sites will be tabulated as a whole and per group.

The numbers of withdrawn subjects will be tabulated according to the reason for withdrawal.

Withdrawal status will be summarised by group using descriptive statistics:

6.1.1. Analysis of safety

The analysis will be performed on the TVC. If the percentage of vaccinated subjects excluded from the ATP cohort for efficacy is at least 10%, a second analysis will be performed on the ATP cohort for efficacy to complement the first analysis.

The percentage of subjects with at least one **local AE** (solicited and unsolicited), with at least one **general AE** (solicited and unsolicited) and with any AE during the 7-day (day 0 – day 6) or the 30-day (day 0 – day 29) follow-up period will be tabulated after each

Statistical Analysis Plan

Study alias & e-track number(s): NTHi-004 (200157)

vaccination and overall with exact 95% confidence interval (CI). The same computations will be done for Grade 3 AEs, for related AEs and for Grade 3 related AEs.

The percentage of subjects/doses reporting each individual solicited local (any grade, Grade 3) and general (any grade, Grade 3, related, Grade 3 related) AE during the 7-day (day 0 to day 6) follow-up period will be tabulated for each group as follows:

- Overall, the percentage of subjects with the symptom and its exact 95% CI.
- Overall, the percentage of doses with the symptom and its exact 95% CI.
- Per study vaccine dose, the percentage of subjects with the symptom and its exact 95% CI.

The exact 95% CIs will be calculated assuming independence between doses. For fever, additional analyses will be performed by 0.5°C increments.

As during the study, some subjects have completed wrong diary cards (paediatric ones instead of adults), a sensitivity analysis will be done on subjects that have completed the correct diary cards to be sure that they were no impact on results.

The verbatim reports of **unsolicited** symptoms will be reviewed by a physician and the signs and symptoms will be coded according to the MedDRA Dictionary for Adverse Reaction Terminology. Every verbatim term will be matched with the appropriate preferred term (PT). The percentage of subjects with unsolicited symptoms during the 30-day follow-up period after any study vaccine dose with its exact 95% CI will be tabulated by group and by MedDRA PT. Similar tabulation will be done for the percentage of doses, for Grade 3 unsolicited symptoms, for unsolicited symptoms that resulted in a medically attended visit, for Grade 3 and causally related unsolicited symptoms and for unsolicited symptoms causally related to vaccination.

For each group and for each **haematology/ biochemistry parameter**:

- The percentage of subjects having results below or above the local laboratory normal ranges will be tabulated by time point.
- The maximum grading from Screening up to study conclusion will be tabulated. Grades will be based on the FDA Guidance for Industry “Toxicity Grading Scale for Healthy Adults and Adolescent Volunteers Enrolled in Preventive Vaccine Clinical Trials” (see Appendix C of the protocol).

The number of subjects who experienced any **pIMD** or any **SAE** from from first vaccination up to 6 months post-Dose 2 will be reported will be reported.

The number of subjects who experienced any **AE leading to study withdrawal**, from first vaccination up to study conclusion, or any **SAE related to study participation of**

Statistical Analysis Plan

Study alias & e-track number(s): NTHi-004 (200157)

concurrent GSK medication/ vaccination, during the entire study period, will be reported.

Pregnancy reports from first vaccination up to 6 months after last vaccination and pregnancy outcomes will be described in detail.

The percentage of subjects/ dose using **concomitant medication/ product** (any medication/ product, any antipyretic and any antipyretic taken prophylactically, respectively) during the 7-day follow-up period (day 0 – day 6) and during the 30-day follow-up period (day 0 – day 29) will be summarised per group for each dose and overall per dose.

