- Chronic use of antibiotics for prevention of AECOPD (*e.g.* azithromycin).
- Receiving oxygen therapy.
- Planned lung transplantation.
- Planned/ underwent lung resection surgery (*e.g.* lung volume reduction surgery or lobectomy).
- Diagnosis of α -1 antitrypsin deficiency as the underlying cause of COPD.
- Diagnosed with a respiratory disorder other than COPD (such as sarcoidosis, active tuberculosis, clinically significant bronchiectasis, lung fibrosis, pulmonary embolism, pneumothorax, current diagnosis of asthma in the opinion of the investigator), or chest X-ray/ CT scan revealing evidence of clinically significant abnormalities not believed to be due to the presence of COPD. Subjects with allergic

rhinitis do not need to be excluded and may be enrolled at the discretion of the investigator.

- History of any reaction or hypersensitivity likely to be exacerbated by any component of the vaccines and/ or the bronchodilator used for spirometry assessment during the study.
- Contraindication for spirometry testing (such as recent eye surgery, recent thoracic or abdominal surgery procedures, unstable cardiovascular status, recent myocardial infection or pulmonary embolism).
- Clinically significant* abnormality in haematology (haemoglobin, platelets or WBC) or biochemistry parameter (ALT, AST or creatinine), as per the judgement of the investigator.

* As the study participants are COPD patients, various pre-existing haematological/biochemical abnormalities might be detected. The investigator should use his/ her clinical judgement to decide which ones are clinically significant.

- Acute cardiac insufficiency.
- Malignancies within the previous 5 years (excluding non-melanotic skin cancer and carcinoma *in situ* of the cervix, if considered cured) or lymphoproliferative disorder.
- Any known disease or condition likely to cause death during the study period.
- Acute disease and/ or fever at the time of Screening.
 - Fever is defined as oral or axillary temperature $\geq 37.5^{\circ}\text{C}$. The preferred route for recording temperature in this study will be oral.
 - Subjects with acute disease and/ or fever at the time of Screening may be enrolled at a later date if enrolment is still open. Subjects with a minor illness without fever may be enrolled at the discretion of the investigator.
- Pregnant or lactating female.
- Current alcoholism and/ or drug abuse.

Refer to the [glossary of terms](#) for the definition of alcoholism.

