6.2.2.2. Treatment allocation to the subject

The treatment numbers will be allocated by dose.

6.2.2.2.1. *Study group and treatment number allocation*

The target will be to enrol approximately 140 eligible subjects who will be randomly assigned to the 2 study groups in a (1:1) ratio (approximately 70 subjects in each group).

Allocation of a subject to a study group at the investigator site will be performed using a centralised randomisation system on the internet (SBIR). The randomisation algorithm will use a minimisation procedure accounting for age (40 - 59 years or 60 - 80 years), number of moderate/ severe AECOPD in the previous year (< 2 or \geq 2) and GOLD grade (GOLD 2 or GOLD 3). All factors will have equal weight in the minimisation algorithm.

At Visit 1, before administration of vaccine Dose 1 to eligible subjects who signed and dated the ICF at the Screening Visit, the dedicated site staff will access SBIR. Upon providing the subject's age category (40 - 59 years or 60 - 80 years), number of moderate/ severe AECOPD in the previous year and his/ her GOLD grade, the randomisation system will determine the study group and will provide the treatment number to be used for the first dose.

The number of each administered treatment must be recorded in the eCRF on the Vaccine Administration screen.

When SBIR is not available, refer to the SBIR user guide or the SPM for specific instructions.

6.2.2.2.2. *Treatment number allocation for subsequent doses*

For each dose subsequent to the first dose, the dedicated study staff will access SBIR. Upon providing the subject identification number, the system will provide a treatment number consistent with the allocated study group.

The number of each administered treatment must be recorded in the eCRF on the Vaccine Administration screen.

When SBIR is not available, refer to the SBIR user guide or the SPM for specific instructions.

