11.4. Determination of sample size

This study is a Phase II safety study to assess safety and reactogenicity of the investigational vaccine in moderate and severe COPD patients.

Considering the sample size of 70 in the group 10-AS01E, [Figure 4](#) illustrates the probability of detecting an AE with true occurrence rate 0 - 10%.

Figure 4 Probability not to observe an AE for 60, 70 or 80 subjects per group

From [Figure 4](#), it can be seen that with a sample size of 70 subjects per group, there is more than 50% of chance to detect an AE with a true incidence of 1%, and more than 97% of chance to detect an AE with a true incidence of 5%.

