11.14.2. Statistical considerations for interim analyses

All analyses are descriptive, and performed on final or as clean as possible data therefore no adjustment needs to be performed.

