In the development of the toxicity grading scales for healthy volunteers, we chose parameter limit values based on published information, when such values were available (Refs. 1-6). For example, the Brighton Collaboration has developed case definitions and guidelines to evaluate some adverse events associated with administering vaccines (Ref. 3). In some cases, parameter limit values were based on clinical experience and experience reviewing vaccine clinical trials that enroll normal healthy subjects.

Toxicity grading scales for laboratory abnormalities should consider the local laboratory reference values when the parameter limit values are defined. The characterization of laboratory parameters among some populations of healthy adults and adolescents may require the exercise of clinical judgment, for example, consideration of the potential for ethnic differences in white blood cell (WBC) counts or gender differences in creatine phosphokinase (CPK) values.

iii. TOXICITY GRADING SCALE TABLES

Adverse events in a clinical trial of an investigational vaccine must be recorded and monitored and, when appropriate, reported to FDA and others involved in an investigation (sponsors, IRBs, and investigators). (See, for example, 21 CFR 312.32, 312.33, 312.50, 312.55, 312.56, 312.60, 312.62, 312.64, and 312.66). Although the use of a toxicity grading scale for adverse events would not replace these regulatory requirements, using a scale to categories adverse events observed during a clinical trial may assist you in monitoring safety and making required reports. Nonetheless, we believe that categorization or grading of data as outlined in this document is supplementary to and should not replace full and complete data analysis.

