7.1.3. Immunogenicity

- For a given subject and the analysis of a given immunogenicity measurement, missing or un-evaluable measurements will not be replaced.
- A seronegative subject is defined as a subject whose antibody concentration is below the assay cut-off value.
- A seropositive subject is defined as a subject whose antibody concentration is greater than or equal to the assay cut-off value.
- Antibody concentrations below the assay cut-off will be given an arbitrary value of half the assay cut-off for the purpose of geometric mean concentration (GMC) calculation.
- Calculation of the GMCs will be performed by taking the anti-logarithm in base 10 (anti-log10) of the mean of the log10 concentration transformations.

Statistical Analysis Plan

Study alias & e-track number(s): NTHi-004 (200157)

- The assay cut-off is the value under which there is no quantifiable result for which no accuracy and precision can be reported. For an assay with a specific 'cut_off' , numerical immuno result is derived from a character field (rawres):
 - If rawres is 'NEG' or '-' or '(-)', numeric result= cutt_off/2,
 - if rawres is 'POS' or '+' or '(+)', numeric result = cut_off,
 - if rawres is '< value' and value<=cut_off, numeric result =cut_off/2,
 - if rawres is '< value' and value>cut_off, numeric result =value,
 - if rawres is '> value' and value<cut_off, numeric result =cut_off/2,
 - if rawres is '> value' and value>=cut_off, numeric result =value,
 - if rawres is '<= value' or '>= value' and value<cut_off, numeric result =cut_off/2,
 - if rawres is '<= value' or '>= value' and value>=cut_off, numeric result =value,
 - if rawres is a value < cut_off, numeric result = cut_off/2,
 - if rawres is a value >= cut_off, numeric result = rawres,
 - else numeric result is left blank.
- All CI computed will be two-sided 95% CI.

Impact of the investigational vaccine on AECOPD

- For a given subject and the analysis of a given laboratory assay, missing or un-evaluatable measurements will not be replaced.
- Subjects who did not have any sputum collected during at least 1 AECOPD (if at least 1 AECOPD occurred) will not be taken into account for the NTHI-associated AECOPD analyses.

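### Quantitative safety laboratory values are reported only as out-of-range percentages and maximum grades, so movement within the normal range or within one grade is not shown

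*SAP*

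**What the plan says.** Occurrence of each haematological or biochemical abnormality, at Day 0 and seven later time points, is one of the six primary endpoints (Protocol 11.1; SAP 4.1). Protocol Table 11 lists haemoglobin, platelets, white cells (with differential), ALT, AST and creatinine as quantitative. Table 10 schedules them at Screening and Days 0, 7, 30, 60, 67, 90, 270 and 450.

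SAP Amendment 1 section 6.1.1 and Protocol 11.8 give two analyses per group and parameter:

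- "The percentage of subjects having results below or above the local laboratory normal ranges will be tabulated by time point";
- the maximum grade from Screening to study conclusion, on the FDA scale reproduced in Protocol Appendix C.

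The guidance text in Appendix C says that "categorization or grading of data as outlined in this document is supplementary to and should not replace full and complete data analysis". Protocol 5.3, explaining why clinical significance at entry is left to the investigator, notes that in these patients "various pre-existing haematological/biochemical abnormalities might be detected".

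Other quantitative measurements are treated differently. Biomarkers (Protocol 11.12; SAP 6.1.6), cell-mediated responses (SAP 6.1.2), and quality of life, FEV1 and walk-test scores (SAP 6.1.5) receive descriptive statistics. Antibody concentrations receive a baseline-adjusted comparison (SAP 6.1.2).

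**The concern.** Both planned displays cut a quantity into categories. A value that moves substantially but stays in its category changes neither of them. Because the maximum grade is taken from Screening onward, an abnormality present before vaccination can set a subject's maximum and cover any later change up to that grade. With pre-existing abnormalities expected at entry, a subject's movement from his or her own Day 0 value is the natural description, and it is not planned.

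At stake is how fully the study meets its primary objective of describing safety, in the vaccine's first use in moderate and severe COPD. A moderate systematic shift, for example at Day 7 or Day 67, could be present in the database and show only faintly in the report.

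**Working it through.** **The plan's own figure.** Protocol 11.4 gives no calculation for laboratory values. Its only figure is the chance of seeing at least one adverse event among 70 subjects, 1 − (1 − p)^70. For p = 1% this is 1 − 0.99^70 = 50.5%, and for p = 5% it is 1 − 0.95^70 = 97.2%. Both agree with the stated figures of more than 50% and more than 97%.

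**What the two displays miss, on the plan's own scale (Table 27).**

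- ALT rising from 1.2 to 2.4 × ULN is above range and Grade 1 (1.1–2.5 × ULN) before and after. Neither display changes.
- ALT rising from 0.3 to 0.9 × ULN is never above range and never graded.
- Creatinine rising from 0.7 to 1.4 mg/dL is ungraded, since Grade 1 starts at 1.5. Whether it is out of range depends on the laboratory's limits, which the documents do not give.
- Haemoglobin is the exception. It has change-from-baseline rows for both sexes, and any fall counts as at least Grade 1. Whether baseline means Screening or Day 0 is not stated.

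**How much information the cut costs.** From the documents: "Considering the sample size of 70 in the group 10-AS01E", subjects "randomly assigned to the 2 study groups in a (1:1) ratio", and "All CI computed will be two-sided 95% CI", used here as a two-sided 5% level for illustration only. Assumed, because the documents give nothing: normally distributed values, a fraction p1 of controls beyond one limit, and a vaccine shift of d SD.

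- Cut-point: c = z(1 − p1). Vaccine fraction beyond the limit: p2 = 1 − Φ(c − d).
- Power on percentages: Φ[(p2 − p1 − 1.96·se0)/se1], with se0 from the pooled proportion and se1 from the separate ones.
- Power on means: Φ[d/√(2/70) − 1.96]. Adjusting for Day 0 at correlation r divides the SD by replacing it with √(1 − r²).

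Example with p1 = 2.5%, d = 0.5: c = 1.960, p2 = 1 − Φ(1.460) = 7.2%, se0 = 0.0364, se1 = 0.0361. Power = Φ[(0.047 − 1.96 × 0.0364)/0.0361] = 25%. On means: Φ(0.5/0.169 − 1.96) = Φ(1.00) = 84%. With Day 0 adjustment it is 92.7% at r = 0.5 and 98.5% at r = 0.7.

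| Controls out of range | Shift (SD) | Vaccine out of range | Expected subjects, control v vaccine | Power, percentage | Power, means |
|---|---|---|---|---|---|
| 2.5% | 0.5 | 7.2% | 1.8 v 5.1 | 25% | 84% |
| 5% | 0.5 | 12.6% | 3.5 v 8.8 | 35% | 84% |
| 10% | 0.5 | 21.7% | 7.0 v 15.2 | 48% | 84% |
| 2.5% | 0.75 | 11.3% | 1.8 v 7.9 | 54% | 99% |
| 5% | 0.75 | 18.5% | 3.5 v 13.0 | 70% | 99% |
| 10% | 0.75 | 29.8% | 7.0 v 20.8 | 84% | 99% |
| 2.5% | 1.0 | 16.9% | 1.8 v 11.8 | 83% | >99% |
| 5% | 1.0 | 26.0% | 3.5 v 18.2 | 94% | >99% |
| 10% | 1.0 | 38.9% | 7.0 v 27.2 | 98% | >99% |

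Simulating the Pearson chi-square (20,000 replicates) gives 24%, 36% and 48% for the three 0.5 SD rows. Fisher's exact test gives 12% for the 2.5% row and 40% for the 10% row. The table models the out-of-range percentage at one time point. It does not model the grade display.

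**The case against.** Several stronger readings are tempting, and the documents do not support them.

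- *Day 0 is not used.* It is: Day 0 is a named time point of the endpoint and is tabulated by group, and haemoglobin is graded on change from baseline. What is missing is the within-subject comparison for the other parameters.
- *Shifts across the range are invisible.* They are blunted. At 1 SD the percentage alone has 83–98% power in the table above.
- *A subject abnormal at entry looks the same however much the value moves.* Worsening beyond the subject's highest earlier grade shows in the maximum-grade display. Protocol 9.1.4 also makes clinically significant abnormal findings that are present at baseline and worsen significantly reportable as adverse events.
- *The primary endpoint is not properly analysed.* The endpoint is occurrence of abnormality, and the planned displays match that wording.
- *The study is underpowered for laboratory safety.* Protocol 11.14.2 says "All analyses are descriptive, and performed on final or as clean as possible data". No laboratory test or power is claimed, and every shift above is assumed.
- *The cited guidance requires continuous summaries.* It does not name them, and it describes itself as recommendations.

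Other sources of laboratory information exist, but they do not fill the gap. The internal safety committee sees all available safety data, but no study report is written from its evaluations (Protocol 11.8.1). Individual listings come only at the final step, with unspecified content (SAP 8.1). Holding rule 2c concerns Grade 3 or higher findings. The separate annex of tables and listings is not available here. However, the SAP's opening text assigns the analyses to the SAP itself and only flow and format to the annex.

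What stands is a real but limited loss of information. The objection also bears on the remedy: adjusted intervals for six parameters at seven post-vaccination visits would number 42, of which about 42 × 0.05 = 2.1 would be expected to exclude zero by chance if the vaccine had no effect.

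**Conclusion.** The concern holds as an information gap. For the safety laboratory values the plan contains no level, change from Day 0 or shift table. Movement within the normal range or within one grade goes unshown except for haemoglobin, and moderate shifts across a limit are weakly displayed. In the illustration, a 0.5 SD shift has about 24–48% power on the percentage against 84% on means. By 1 SD the difference is a few points when 5% or more of controls are out of range, and about 17 points (83% against more than 99%) when only 2.5% are. These sizes rest on assumed normality, shifts and out-of-range rates, and on a test that the plan does not make. The planned displays remain valid for the endpoint as worded. This is a cheap improvement to the description of safety and not an error that invalidates the analysis.

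**What to change.** In SAP 6.1.1 and Protocol 11.8 add, by group and parameter:

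- at each post-vaccination visit, n, mean, SD, median and quartiles of the value and of the change from Day 0;
- a shift table from the Day 0 category or grade to the worst post-vaccination category or grade.

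State whether baseline for the haemoglobin change grade is Screening or Day 0. Keep the out-of-range and maximum-grade tables. A Day 0-adjusted group difference with a 95% interval is optional. If it is included, label it descriptive and unadjusted for multiplicity.

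The cost is SAP and protocol wording and a few more tables from data already collected, with no new sampling. If intervals are added, some will exclude zero by chance, and the report should say so.
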